5.7. EVALUATIONS DURING TREATMENT

The following assessments will be done while the patient is on treatment ([Table 6](#)). A 2-day window is allowed for the different tests and procedures (except where otherwise specified).

Table 6. Evaluations during treatment

	ASSESSMENT	TIME
1. Clinical examination	• Complete physical examination. • ECOG PS (Appendix 1).	Day 1 of Cycle 1 prior to the Zalypsis® infusion, and then whenever clinically indicated.
	• Vital signs: heart rate, blood pressure and body temperature.	Before any Zalypsis® infusion.
	• Weight and BSA.	Repeat on Day 1 of each cycle prior to the Zalypsis® infusion, and then whenever clinically indicated.
	• Concomitant disease and treatments.	Throughout the “on-treatment” period*.
2. Laboratory tests	• Hematology: differential WBC (neutrophils, lymphocytes), hemoglobin and platelets. • Biochemistry A: liver function tests (ALT, AP, AST, LDH, total bilirubin), creatinine, CPK, troponin I**, glucose, and serum electrolytes (Na ⁺ , Cl ⁻ , K ⁺ , Ca ⁺⁺ , Mg ⁺⁺).	Repeat on Days 1, 8 and 15 of each cycle prior to Zalypsis® infusion. If NCI-CTCAE grade ≥ 3 occurs, the appropriate test(s) should be repeated at least every 2-3 days until recovery to grade ≤ 1 or baseline. In case of febrile neutropenia (any grade) ANC determination must be repeated every day until resolution.
	• Biochemistry B: total protein and albumin.	Repeat on Day 1 of each cycle prior to Zalypsis® infusion, and then whenever clinically indicated. If NCI-CTCAE grade ≥ 3 occurs, the appropriate test(s) should be repeated at least every 2-3 days until recovery to grade ≤ 1 or baseline.
3. Calculated creatinine clearance	Calculated according to Cockcroft and Gault's formula (Appendix 4).	Repeat on Day 1 of each cycle prior to the Zalypsis® infusion, and then whenever clinically indicated.
4. ECG**		ECG must be repeated prior to administration of each Zalypsis® infusion and if clinically indicated.
5. LVEF**	ECHO.	Repeat every other cycle, with a 1-week window, and if clinically indicated.
6. Pregnancy test, if applicable		Every four weeks during treatment and three months after last Zalypsis® administration.

	ASSESSMENT	TIME
7. AEs	As per NCI-CTCAE v. 4.0.	Throughout the “on-treatment” period*. Patients withdrawn with Zalypsis®-related ongoing AEs must be followed up with the appropriate tests until event resolution.

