5.8. EVALUATION AT END OF TREATMENT

The end-of-treatment visit will be scheduled at 30 days after the last Zalypsis® infusion (a window of \pm 2 days is allowed).

Regardless of the reason for the discontinuation, the same complete workup conducted before study entry (except for medical history) will have to be done at this end-of-treatment visit. This will include the following assessments:

- Complete physical examination.
- Vital signs.
- ECOG PS.
- Weight and BSA, if clinically indicated.
- Hematology.
- Biochemistry A.
- Biochemistry B.
- Calculated creatinine clearance, if clinically indicated.
- Pregnancy test, if applicable.
- ECG and LVEF by ECHO.

- Concomitant diseases and treatments.
- Safety assessment (AEs).
- Tumor assessment.
- Other tests (when indicated, according to the clinical and laboratory context).

Adverse events must be reported until 30 days after the last study drug administration. All serious adverse events (SAEs) occurring within 30 days of the last study drug administration will be reported. Beyond this period of time, only those SAEs suspected to be treatment-related will be reported (see Section [9](#)).

The Sponsor(s) will evaluate all safety information that is spontaneously reported by an Investigator beyond the time frame specified in the protocol.

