5.9. FOLLOW-UP AFTER END-OF-TREATMENT VISIT

The date and reason of the study discontinuation will be recorded on the patient's CRF (see Section [5.2.1.1](#)).

Patients who discontinue treatment without progression will be followed every three months until disease progression, other antitumor therapy or death or until the date of study termination, whichever occurs first. After disease progression or after other antitumor therapy, patients will be followed every three months until death, or until the date of study termination, whichever occurs first.

Patients' follow-up determinations will include: ECOG PS, vital signs, complete physical examination, weight if clinically indicated, hematology, biochemistry A and B, concomitant diseases and treatment, calculated creatinine clearance if clinically indicated, and tumor assessment.

Follow-up of cardiac assessments (including ECG and LVEF) should be performed at three and six months after end of treatment.

Patients who withdraw consent will not be followed with any study procedures.

Patients withdrawn with ongoing Zalyps[®]-related AEs (including SAEs) will be followed-up until the events or their sequelae resolve or stabilize at a level acceptable to the Investigator and the Sponsor(s).

Additional parameters will be assessed and/or the frequency of observations will be increased at the Investigator's discretion and according to the nature of the observed AEs. In case of death, when available, autopsy data should be provided.

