7.4.6. Other safety evaluations

Physical examination evaluation (normal/abnormal) and vital signs at baseline and during treatment will be described by means of frequency counts and summary statistics.

Electrocardiogram (ECG) evaluation (normal/abnormal) will be summarized with frequency counts

Continuous variables (LVEF and LVEF Normal Range) will be summarized and presented with summary statistics, i.e., mean, standard deviation, median and range.

Tabulation of baseline values and evolution during treatment will be presented for PS, weight, and LVEF, troponin I measurement.

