12.3.2. Biochemical abnormalities

Table 12.3.2.1 Biochemical abnormalities during treatment, worst grade per patient.

Parameter*	Gra	de 1	Gra	de 2	Gra	de 3	Gra	de 4	Total (G1-G4)
Parameter.	N	%	N	%	N	%	N	%	N	%
AST										
ALT										
*										

Programming Notes: Percentages are based on the safety population. (*) All biochemical abnormalities susceptible to be graded by NCI-CTCAE v4.0.

Table 12.3.2.2 Biochemical abnormalities during treatment, worst grade per cycle.

Doromotor*	Gra	de 1	Gra	de 2	Gra	de 3	Gra	de 4	Total (G1-G4)
Parameter*	N	%	N	%	N	%	N	%	N	%
AST										
ALT										
*										

Programming Notes: Percentages are based on the safety population. (*) All biochemical abnormalities susceptible to be graded by NCI-CTCAE v4.0.

Table 12.3.2.3 Supportive listing: Patients with any biochemical abnormalities grade 3-4.

Patient	Cycle	Event/	Value	Grade	Onset	Onset	*	Days with
ID	Cycle	Parameter	at BL	at BL	day	value	••••	Grade 3-4

(*) Nadir day, nadir value, recovery date, recovery value and recovery grade to grade ≤ 2 .

Table 12.3.2.4 Listing of patients and cycles with biochemical evaluations missing.

	Patient ID	Cycle	Lab test
--	------------	-------	----------

Table 12.3.2.5 Time course and recovery from biochemical toxicities.

		All cyc	les
	N	Median	Range
ALT			
Day of peak ALT count			
Peak of ALT count (/mm ³)			
Day of ALT G3-4 onset			
Day of recovery to grade ≤2			
Number of days with grade 3-4 ALT increase			
AST			

Day of peak AST count Peak of AST count (/mm³) Day of AST G3-4 onset

Day of recovery to grade ≤2*

Number of days with grade 3-4 AST increase

Programming notes: (*) Denominator= Number of cycles with Grade 3-4. Also recovery to grade 1 if required.

Table 12.3.2.6 Baseline grade and evolution of biochemical toxicities.

			Wo	orst grac	de per p	atient d	luring t	reatmen	t	
Dagalina	Grade 0		Grade 1		Gra	de 2 Gra		le 3	Gra	de 4
Baseline	N	%	N	%	N	%	N	%	N	%
AST										
Grade 0										
Grade 1										
Grade 2										
Grade 3										
Grade 4										
ALT										
Grade 0										
Grade 1										
Grade 2										
Grade 3										
Grade 4										

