Criteria, Action ta Table 12.6.2 Listi Patient ID Table 12.6.3 Listi Patient ID	ken ing of ECG ev Baseline ing of patients Renformation ob	Cycle 1 Cycle 1 with abnormal esult at baselin tained from AE LVEF (%).	ent. Cycle ECG. e	2 Cycle	Cycle (X) Specify*
Criteria, Action ta Table 12.6.2 Listi Patient ID Table 12.6.3 Listi Patient ID (*) If applicable in	ken ing of ECG ev Baseline ing of patients Renformation ob	Cycle 1 S with abnormal esult at baselin tained from AE	ent. Cycle ECG.	2	Cycle (X)
Criteria, Action ta Table 12.6.2 Listi Patient ID Table 12.6.3 Listi Patient ID (*) If applicable in	ken ing of ECG ev Baseline ing of patients Renformation ob	Cycle 1 Cycle 1 with abnormal esult at baselin tained from AE LVEF (%).	ent. Cycle ECG. e	2 Cycle	Cycle (X) Specify*
Criteria, Action ta Table 12.6.2 Listi Patient ID Table 12.6.3 Listi Patient ID (*) If applicable in	ken ing of ECG ev Baseline ing of patients R nformation ob	Cycle 1 Gwith abnormal esult at baselin tained from AE LVEF (%).	ent. Cycle ECG. e Median	2 Cycle	Cycle (X) Specify*
Criteria, Action ta Table 12.6.2 Listi Patient ID Table 12.6.3 Listi Patient ID (*) If applicable in Table 12.6.4 Med	ken ing of ECG ev Baseline ing of patients R nformation ob	Cycle 1 Gwith abnormal esult at baselin tained from AE LVEF (%).	ent. Cycle ECG. e Median	Cycle Min	Cycle (X) Specify*
Criteria, Action ta Table 12.6.2 Listi Patient ID Table 12.6.3 Listi Patient ID (*) If applicable in Table 12.6.4 Med Table 12.6.5 Listi	ing of ECG events and the second seco	Cycle 1 with abnormal esult at baselin tained from AE LVEF (%). N ECG evolution p	ent. Cycle ECG. e Median per patient.	Cycle Min	Cycle (X) Specify* Max

Table 12.6.6 LVEF characteristics per patient.

Patient ID.	Value at baseline	Minimum value	Cycle (minimum value)

Table 12.6.7 Median change in Troponin I.

	N	Median	Min	Max
Baseline to nadir value (%)				
Baseline to last value (%)				

(*) Also tables in (x ULN) values if applicable.

Table 12.6.8 Listing of Troponin I evolution.

Patient ID.	Value* at Baseline (ng/ml)	Cycle 1	Cycle 2		Cycle (X)
-------------	----------------------------	---------	---------	--	-----------

(*) Also tables in (x ULN) values if applicable

Table 12.6.9 Troponin I characteristics per patient.

Patient ID.	Value* at baseline (ng/ml)	Maximum value	Cycle (maximum value)
-------------	-------------------------------	---------------	-----------------------

(*) Also tables in (x ULN) values if applicable

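### SAP Table 12.6.7 summarises troponin I change to nadir and to last value but not to maximum, so read literally it reports the wrong extreme and misses a rise that has resolved (minor).

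*SAP*

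**What the plan says.** Table 12.6.7 in SAP Section 12.6 gives N, median, minimum and maximum across patients for two quantities: "Baseline to nadir value" and "Baseline to last value", both in percent. A footnote adds a version in multiples of ULN if applicable. It does not add a row for the highest value.

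Other parts of the SAP treat the same or similar measurements differently:
- Table 12.6.9 lists, for each patient, the baseline troponin I, the maximum and the cycle in which it occurred ("Cycle (maximum value").
- Table 12.6.6 lists the minimum LVEF for each patient, which is the adverse direction for LVEF.
- Table 12.3.2.5 describes liver enzymes by their peak ("Day of peak ALT count").
- The footnote to Table 12.3.2.3, the listing of grade 3-4 biochemical abnormalities, speaks of nadir day and nadir value, although some of those analytes do harm by rising.

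The protocol places troponin I in Biochemistry A. Section 5.7, Table 6, says of that panel: "Repeat on Days 1, 8 and 15 of each cycle prior to" the infusion. It is taken again at the end of treatment (Section 5.8: "The end-of-treatment visit will be scheduled at 30 days after the last" infusion) and in follow-up (Section 5.9: "hematology, biochemistry A and B, concomitant diseases and treatment").

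**The concern.** The cardiac signal that the protocol describes is upward. Section 1.2.5 says that phase I cardiac findings were troponin I elevations without other symptoms. It reports four grade 4 increases in the phase I study that used this schedule. A summary of troponin change should therefore show how far values rose. Change to the lowest value cannot show that. Change to the last value shows it only if the rise is still present then.

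Other aggregate tables may not fill the gap:
- Table 12.2.1.3 is limited to six named analytes, and troponin I is not one of them.
- The adverse event tables count a laboratory rise only if it meets the recording criteria in Protocol 9.1.1 and 9.2.1: symptoms, a change in dosing or other treatment, a serious outcome, or the investigator's opinion. An asymptomatic rise that resolves without consequence is the least likely to qualify.
- Table 12.3.2.1 counts worst grades for gradable biochemistry and may include troponin I, but the SAP does not say so. The analyte list in the matching baseline footnote (Table 11.1.7.1) omits troponin I, and Appendix V gives it a listing separate from biochemistry.

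At stake is one descriptive summary of cardiac safety, which could look flat when some patients had a transient rise.

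**Working it through.** The plan states no figure to reproduce here. The check is on what the two rows can show.

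**Step 1. Logic of the rows.** For each patient, percent change = 100 × (value − baseline) / baseline, taken at the lowest, last and highest post-baseline value. The profiles are assumed, with a baseline of 0.02 ng/ml; they test the logic and do not predict values.

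| Assumed course | Post-baseline samples (ng/ml) | To nadir | To last | To maximum |
|---|---|---|---|---|
| No rise | 0.02, 0.02, 0.02 | 0% | 0% | 0% |
| Rise, resolved | 0.02, 0.50, 0.10, 0.02 | 0% | 0% | +2400% |
| Early dip, then rise, resolved | 0.01, 0.50, 0.02 | −50% | 0% | +2400% |
| Rise, partly resolved | 0.02, 0.50, 0.10 | 0% | +400% | +2400% |
| Rise, unresolved | 0.02, 0.10, 0.50 | 0% | +2400% | +2400% |

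For the peak of 0.50: 100 × (0.50 − 0.02) / 0.02 = 2400%. A patient whose rise has resolved gives the same two entries, 0% and 0%, as a patient with no rise. A rise still present at the last sample does show, in part or in full. The Max column does not help, because it is the largest nadir change or last change across patients, not any patient's change to peak.

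**Step 2. Wording within the SAP.** For troponin I, Table 12.6.9 says maximum. For ALT and AST, Table 12.3.2.5 says peak. Against these, the Table 12.3.2.3 footnote uses nadir for biochemistry in general. So the author may have meant worst value, but a programmer working from the Table 12.6.7 label would compute the minimum.

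**Step 3. How many patients might be involved.** Protocol 1.2.5 reports two patients with a grade 4 troponin I increase at 2.0 mg/m². Section 1.2.5.1.1 reports no troponin increase at the recommended dose, which Section 1.2.5.1 sets at 2.0 mg/m² with 24 treated patients. The documents therefore give a range, 0/24 to 2/24. If it carried over (an assumption):
- full trial: 0/24 × 29 = 0 to 2/24 × 29 = 2.4 patients;
- stop at stage 1: 0/24 × 12 = 0 to 2/24 × 12 = 1.0 patient.

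The median of 29 values is the 15th in order, so two or three large rises would barely shift it even in a correct maximum row. The Max column of that row, and counts by worst grade, would show them.

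**The case against.** The best defence is that *nadir* here means worst value. The Table 12.3.2.3 footnote supports this, and if it is right the peak is already in the first row. That makes a labelling slip likely. It does not settle the reading, because the SAP uses maximum and peak elsewhere for quantities that rise. The label needs correcting either way.

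The second defence is that nothing is lost. This stands. Table 12.6.8 gives troponin I by cycle, Table 12.6.9 gives each patient's maximum, and Listing 14.1.19 gives the data. The protocol also has external cardiologists review all troponin I determinations, and Biochemistry A tests of grade 3 or higher are repeated every 2-3 days until recovery. In a trial of 12 or 29 evaluable patients, a reader can see every peak. These are per-patient displays, though, and the aggregate table still reports the wrong extreme.

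Three stronger readings are tempting, and the documents do not support them:
- *That the table breaks the promise in SAP 7.4.6.* That section says: "Tabulation of baseline values and evolution during treatment will be presented for PS, weight, and LVEF, troponin I measurement". Table 12.6.8 runs from baseline through each cycle and meets it.
- *That the last-value row is mostly an off-drug value.* The SAP does not define last value. It could be the last pre-infusion sample, the end-of-treatment sample or a follow-up sample.
- *That about 8% of patients should be expected to have a grade 4 rise.* The figure 4/49 = 8.2% pools all phase I doses from 0.07 to 3.0 mg/m², and two of the four cases were above 2.0 mg/m². At 2.0 mg/m² the documents themselves give anything from none to two of 24.

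**Conclusion.** The point holds as a minor table-shell error. Read literally, Table 12.6.7 summarises the wrong extreme for troponin I, and a rise resolved by the last sample shows in neither row. If *nadir* was meant as worst value, the fault is only an ambiguous label.

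The table is descriptive and feeds no endpoint, sample size or decision rule. On the phase I range, 0 to about 2.4 of 29 patients, or 0 to 1 of 12, would have a grade 4 rise. This assumes that the rate at 2.0 mg/m² carries over. It counts evaluable patients only; the treated population may be larger because non-evaluable patients are replaced. Only rises that had resolved by the last sample would go unseen in the table.

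A reader might infer that troponin peaks would go unreported. They would not, since three other outputs show them patient by patient.

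One background item is separate and does not bear on this grading. Protocol 1.2.5 (two grade 4 troponin I increases at 2.0 mg/m²) and Protocol 1.2.5.1.1 (no troponin increases at the recommended dose) cannot both stand as written. Some neighbouring background text was not in the copy reviewed and may bear on this.

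**What to change.** In Table 12.6.7, replace the nadir row with change from baseline to maximum value (%), also in multiples of ULN. Keep the last-value row and the Min and Max columns.

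Two clarifications are optional:
- Add a footnote saying which samples count as last value: on-treatment only, end of treatment, or follow-up.
- Confirm that Table 12.3.2.1 counts troponin I by worst CTCAE grade. A count shows a few affected patients better than a median does.

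Separately, reconcile Protocol 1.2.5 and 1.2.5.1.1 against the phase I data.

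The cost is one relabelled row and, if the options are taken, one footnote and one analyte named in an existing table. The background check needs only the phase I data. No new data collection is needed, and no primary or secondary analysis changes.

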12.7. Other tests and procedures

Table 12.7.1.1 Other tests and procedures.

Patient ID.	Cycle	Test Date	Test name	Result(Normal/Abnormal)	Findings

13. Appendix IV. Figures

NOTE: Figures here showed are examples and may vary in the format and will be showed for "all evaluable patients" and "all treated patients" when applicable.

Figure 13.1 Evolution of laboratory abnormalities (ANC, Platelets, AST, ALT,.....)

[figure not shown]

Figure 13.2 Overall survival.

[figure not shown]

Figure 13.3 Progression-free survival.

[figure not shown]
[figure not shown]
[figure not shown]

Figure 13.4 Duration of response.

[figure not shown]
Kaplan-Meier curve of duration of response (if any response is observed).

Figure 13.5 Waterfall plots.

[figure not shown]
Maximum tumor shrinkage in measurable lesions by RECIST v1.1 will be displayed. Additional graphs by histology or RECIST response will also be provided when applicable.

Figure 13.6 Spider plot (SLD)

(*) Sum of longest diameters for all target lesions.

Figure 13.7 Boxplot of LVEF evolution from BL.

Boxplot showing the change in LVEF from baseline, to worst value by cycle.

14. Appendix V. DB listings.

- -Listing 14.1.1. Cover
- -Listing 14.1.2. Study registration
- -Listing 14.1.3. Demography
- -Listing 14.1.4. Pregnancy test
- -Listing 14.1.5. Prior history
- -Listing 14.1.6. Ewing sarcoma history
- -Listing 14.1.7. Prior anticancer therapy: surgery
- -Listing 14.1.8. Prior anticancer therapy: radiotherapy
- -Listing 14.1.9. Prior anticancer systemic therapy: chemotherapy/biological therapy
- -Listing 14.1.10. Drug administration
- -Listing 14.1.11. Hematology laboratory values
- -Listing 14.1.12. Biochemical laboratory values
- -Listing 14.1.13. Other metabolic laboratory values
- -Listing 14.1.14. Physical examination
- -Listing 14.1.15. Performance status
- -Listing 14.1.16. Vital signs
- -Listing 14.1.17. Electrocardiogram
- -Listing 14.1.18. LVEF
- -Listing 14.1.19. Troponin I
- -Listing 14.1.20. Other tests and procedures
- -Listing 14.1.21. Adverse events (including signs and symptoms)
- -Listing 14.1.22. Concomitant therapy/procedures
- -Listing 14.1.23. Antiemetic prophylactic medication
- -Listing 14.1.24. Tumor evaluation
- -Listing 14.1.25. Radiological evaluation response assessment by cycle
- -Listing 14.1.26. Clinical evaluation response assessment by cycle
- -Listing 14.1.27. Overall response assessment by cycle
- -Listing 14.1.28. Best overall response
- -Listing 14.1.29. End of treatment
- -Listing 14.1.30. Follow up
- -Listing 14.1.31. Death report form
- -Listing 14.1.32. Off study
- -Listing 14.1.33. Signature report

15. SAP Version History.

Due to safety reasons, an independent cardiologist will undertake a review of all the ECGs and echocardiograms performed to the patients during the course of the study, in order to evaluate the cardiotoxicity risk of PM00104. This analysis was originally included in the first version of the SAP but due to logistical reasons, this analysis will be performed lately the database analyses, consequently it will be done in a separate document. The Statistical Analysis Plan is changed in accordance to the new version (version 2) as follows:

- All graphs and listings referred in the first version of the statistical plan will be presented in a separate document and will include data from CRF database and independent review database.
- In addition some minor changes and corrections in the text and to the mock shells have been done in order to improve a clear, unambiguous communication of the science and statistics of the trial.

Major changes:

Section 8.7 Independent review committee:

Original text: "Because of safety reasons, an independent cardiologist will undertake a review of all the ECGs and echocardiograms performed to the patients during the course of the study, in order to evaluate the cardiac risk of Zalypsis[®]. For this purpose all tables, graphs and listings will be presented in duplicate and all results will specify from which database are obtained, that is, CRF database and independent review database.

See section 12.6 Cardiac Safety."

Change to: "Because of safety reasons, an independent cardiologist will undertake a review of all the ECGs and echocardiograms performed to the patients during the course of the study, in order to evaluate the cardiotoxicity risk of PM00104. For this purpose, an independent cardiologist's report not included in this SAP will be presented as an Appendix of the CSR"

Section 12.6 Cardiac Safety:

Original text: "As an independent cardiologist will undertake a review of all the ECGs and echocardiograms performed to the patients during the course of the study, tables and listings defined in this section will be duplicated and will have a comprehensive header indication which date base were obtained, i.e, CRF database and Independent review database.

In this section additional tables and listings will be provided under request if clinical interest."

Change to: "As an independent cardiologist will undertake a review of all the ECGs, echocardiograms and troponin I determinations performed to the patients during the course of the study, tables and listings defined in this section will be duplicated and will have a comprehensive header indication which datebase were obtained, i.e, case report form (CRF) database and Independent review database.

In this section additional tables and listings will be provided under request if clinical interest."

Section 13 Appendix IV.

Original text: Figure 13.8 Boxplot of LVEF (baseline, nadir and last value available). **Change to:** Figure 13.8 Boxplot of LVEF (baseline, nadir and last value available).

Section 14 Appendix V.

Original text: Listing 14.1.17 Electrocardiogram*, 14.1.18 LVEF* and Listing 14.1.19 Troponin I* and (*) Also will be included information for the independent review mentioned in section 8.7 of this document.

Change to: Listing 14.1.17 Electrocardiogram, 14.1.18 LVEF and Listing 14.1.19 Troponin I and (*) Also will be included information for the independent review mentioned in section 8.7 of this document.

Section 15 SAP Version History has been included in order to be consistent with the SAP amendment of this study and in accordance with PharmaMar's SOP.
